
≥ Grade 3
	
Hold therapy and resume imatinib at 300 mg QD after recovery to ≤ Grade 1, if recovery occurs within 14 days
 
If toxicity persists for 15-28 days or recurs, hold therapy and resume at next lower dose level after recovery to ≤ Grade 1:
 
I→ 200 mg QD
 
If recurrence is seen at the reduced imatinib dose, hold therapy and resume at next lower dose level after recovery to ≤ Grade 1.
 
I→ 100 mg QD
 
If 4th occurrence, considerations should be had to remove subject from study if the toxicities are not manageable with appropriate supportive measures.

------------------	---

Dose re-escalation

Every attempt to re-escalate the dose of study treatment to the initial dose level should be made. This applies to either dose reductions due to hematological or non-hematological toxicities. The dose should be re-escalated if the following criteria are met within 4 weeks after dose reduction:

- All ≥ Grade 2 non-hematologic toxicities have resolved to ≤ Grade 1
- All ≥ Grade 3 hematologic toxicities have resolved to ≤ Grade 1
- Or alternatively, all ≥ Grade 3 hematological and non-hematological toxicities have resolved to ≤ Grade 2 and are manageable with supportive therapy

Re-escalation of imatinib should be considered and are encouraged, especially if a participant undergoes one full cycle at the modified dose without experiencing the toxicity that caused the dose reduction.

MEMORIAL SLOAN-KETTERING CANCER CENTER
IRB PROTOCOL

IRB#: 14-140 A (7)

9.3.2 BGJ398:

For patients who do not tolerate the protocol-specified dosing schedule, dose adjustments are permitted in order to allow the patient to continue the study treatment. These changes must be recorded on the Dosage Administration Record CRF.

All dose modifications should be based on the worst preceding toxicity. The following guidelines need to be applied:

Each patient will be allowed up to 3 dose reductions, provided this is feasible based on the RP2D. Patients must discontinue BGJ398 if toxicities persist following 3 dose reductions (Table 6) unless a continuation is allowed in discussion with the MSKCC PI.

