Following resolution of toxicity to baseline or \leq grade 1, treatment is resumed at either the same or lower doses of study drugs as per the criteria in Table 6. If treatment is resumed at the same doses of study drugs, and the same toxicity recurs with the same or worse severity regardless of duration, doses must be reduced to the next lower dose level (Table 6). If treatment is resumed at the lower doses of study drugs, and the same toxicity recurs with the same or worse severity, the patient must discontinue study treatment unless a continuation is allowed in discussion with the MSKCC PI.

If a patient requires a dose delay of > 14 consecutive days of BGJ398 from the intended day of the next scheduled dose, then the patient should be discontinued from the study treatment unless a continuation is allowed in discussion with the MSKCC PI.

In exceptional situations, study treatment may continue even if the patient experienced one of the treatment stopping rules. The decision to allow for continuation of treatment will be made on a case-by-case basis following discussion between the MSKCC Principal Investigator (MPI) and the Investigator. Situations that may allow for continuation of treatment include but are not limited to the following. A dose delay of > 14 days has occurred, but the patient is clearly benefiting from study treatment (i.e., stable disease, partial response, or complete response) and it is the investigator's opinion that no safety concerns are present, after discussion with the MPI, the patient may remain on the study treatment. A third or subsequent reduction (to dose level -3) in dose may be allowed if the patient is clearly benefiting from study treatment (i.e., stable disease, partial response, or complete response) but is experiencing adverse events that prevent continued treatment at the already reduced dose.

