For guidance regarding interruptions in BGJ398 therapy due to adverse events, please see Table 7. Of special note is management of hyperphosphatemia, an expected on-target drug effect. See the Renal section of Table 8 for dose interruptions for acute kidney injury accompanied by hyperphosphatemia. Recommendations for prophylaxis and dose modifications for hyperphosphatemia are outlined in Table 8. Exact timing of stopping/starting BGJ398 in the setting of elevated phosphorous levels will be left to the judgment of the treating physician, and differences in phosphate management will not be considered protocol deviations. A list of high-phosphorous foods and suggested alternatives is provided in Appendix F to guide discussions regarding appropriate dietary intake. Please note plasma assessments may substitute for serum assessments per local laboratory standards.

MEMORIAL SLOAN-KETTERING CANCER CENTER
IRB PROTOCOL

IRB#: 14-140 A (7)

Table 6: Dose reduction table

Dose level	BGJ398	
Dose level 0	RP2D	Starting dose
Dose level -1	RP2D minus 25 mg	
Dose level -2	RP2D minus 50mg	
Dose level -3	RP2D minus 75mg	Allowed only if patients is clearly benefiting from study treatment, but is experiencing AE that prevent continued treatment at dose level -2 and applicable based on RP2D

Table 7: Criteria for interruption and re-initiation of BGJ398 treatment

Worst Toxicity CTCAE using the current active CTCAE version	Recommended Dose Modifications any time during a cycle of therapy
Cardiac disorders	
Cardiac - Prolonged QTc interval by Fridericia's Formula (QTcF)	
Grade 1 and 2 : QTcF 481-500 msec (asymptomatic)	Maintain dose level of BGJ398 
 ECG assessments should be performed for 2 additional cycles at the same frequency as in cycle 1, or as clinically indicated. If ECG assessments show no QTcF \geq 481 msec, for subsequent cycles ECG monitoring will be performed as per visit schedule. If ECG assessments are still abnormal (QTcF \geq 481 msec and \leq500 msec), then ECG monitoring must continue at the same frequency as in cycle 1 for all subsequent cycles.

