Fatigue Grade 3	Hold dose of BGJ398 until resolved to CTCAE Grade ≤ 1 
 • If resolved in ≤ 7 days, maintain dose level of BGJ398. • If resolved in > 7 days, discontinue patient from study treatment.
Other clinically significant AEs	
Grade 3	Hold dose of BGJ398 until resolved to CTCAE Grade ≤ 1, then ↓ 1 dose level of BGJ398.
Grade 4	Discontinue patient from study treatment.
All dose modifications should be based on the worst preceding toxicity. Once a dose has been reduced it will not be increased at a later time even if there is no toxicity. Patients who require more than two dose reductions of BGJ398 will be discontinued from study drug treatment. If a patient requires a dose delay of > 14 days from the intended day of the next scheduled dose of BGJ398 then study treatment must be stopped.	

Table 8: Prophylaxis and Treatment recommendations for hyperphosphatemia without kidney injury:

Hyperphosphatemia Prophylaxis (Patients receiving treatment schedule A)	Initiate Sevelamer 800 mg with meals (up to TID) concurrent with BGJ398, unless otherwise contraindicated by patient's current medical condition. Restrict dietary phosphate intake to 600 – 800 mg/day, if BMI ≥ 21kg/m ² .
Hyperphosphatemia Treatment Without Elevated Creatinine	INTERVENTION
Serum Pi > 5.5 – 7.0mg/dL:	Continue sevelamer 800 mg with 2 meals per day and increase the dose of sevelamer with the largest meal to 1600mg (total daily dose = 3200 mg).
Serum Pi 7.1mg – 9.0mg/dL	Increase the dose of sevelamer up to 1600mg (2 tablets per meal) every 8 hours and continue sevelamer through Day 21 and until Serum Pi is <5.5, whichever is later. Sevelamer should be given even on days BGJ398 is not taken until serum Pi is <5.5. If serum Pi ≤ 7.0 mg/dL within 7 days, increase sevelamer to 1600 mg TID with next cycle, if not already done so. No interruption or adjustment to BGJ398 is necessary. If Serum Pi >7.0 mg/dL for longer than 7 days, hold BGJ398 until serum Pi is <5.5 mg/dL. Assess if patients were taking Sevelamer 1600 mg TID on Day 1 of most recent cycle.

MEMORIAL SLOAN-KETTERING CANCER CENTER
IRB PROTOCOL

IRB#: 14-140 A (7)

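### The limit on BGJ398 dose reductions is stated inconsistently: Section 9.3.2 allows each patient up to three, Table 6 makes the third conditional, and the Table 7 note stops treatment beyond two

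*Combined protocol and SAP*

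**What the plan says.** Three statements in the combined protocol and SAP bear on how many times BGJ398 may be reduced.

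- **General rule, Section 9.3.2.** "Each patient will be allowed up to 3 dose reductions, provided this is feasible based on the RP2D". The stopping point follows: "Patients must discontinue BGJ398 if toxicities persist following 3 dose reductions (Table 6) unless a continuation is allowed in discussion with the MSKCC PI".
- **Exceptional situations, Section 9.3.2, and Table 6.** The paragraph opens: "In exceptional situations, study treatment may continue even if the patient experienced one of the treatment stopping rules". Decisions are made case by case after discussion with the lead investigator, and one example is given as: "A third or subsequent reduction (to dose level -3) in dose may be allowed if the patient is clearly benefiting from study treatment". Table 6 defines dose level -3 as "RP2D minus 75mg" and attaches the condition "Allowed only if patients is clearly benefiting from study treatment, but is experiencing AE that prevent continued treatment at dose level -2", adding that it must also be applicable given the RP2D.
- **Closing note to Table 7.** "Patients who require more than two dose reductions of BGJ398 will be discontinued from study drug treatment". The note states no exception and does not refer back to Section 9.3.2 or Table 6.

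**The concern.** A rule for stopping treatment because of toxicity should give one answer for one patient. Here a patient already at dose level -2 who needs a further reduction is covered by three passages with three different outcomes. A site that works from Table 7 at the bedside sees a flat limit and no sign that an exception exists. A site that works from the general text of Section 9.3.2 sees an allowance of three.

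The situation is foreseeable. Hyperphosphatemia suspected to be drug-related was reported in 71.3% of patients in the earlier BGJ398 study (Section 3.2.3.1), and Table 8 prescribes BGJ398 reductions for it in some circumstances. Section 7.0 names three recruiting institutions. At stake are patient safety, protocol compliance and evenness of exposure to the combination. Uneven stopping could also reach the response and PFS data, because Section 12.1.9 requires a claimed response to be met again at least 4 weeks later.

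**Working it through.** The plan gives no statistical figure for this point, so the check is a comparison of text plus one piece of arithmetic on Table 6.

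**Step 1. One patient, three passages.** Take a patient at dose level -2 with toxicity that calls for another reduction.

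- *General rule:* the reduction is available if the RP2D leaves a dose to reduce to. The lead investigator comes in only after the third reduction has failed.
- *Exception paragraph and Table 6:* the reduction is available only with clear benefit. The paragraph treats it as a case-by-case exception.
- *Table 7 note:* the patient is discontinued.

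**Step 2. Which pairs can be reconciled?**

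- *Table 7 note with the exception paragraph and Table 6:* yes. The exception covers any of the treatment stopping rules and names a third reduction as an example. Read together, they give two by default and a third by exception.
- *Table 7 note with the general rule:* no. Under the general rule a third reduction is part of each patient's ordinary allowance, so there is nothing for an exception to permit. The stopping point is three in one place and two in the other.
- *General rule with Table 6:* not as written. The general rule's only condition is feasibility given the RP2D, whereas Table 6 adds clear benefit.

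**Step 3. When does the difference matter?** Inputs: the candidate BGJ398 doses in Table 1 (25, 50, 75, 100 and 125 mg) and the 25 mg steps in Table 6. The dose after k reductions is RP2D − 25k mg, for k = 1, 2, 3. A reduction is feasible if the result is above zero.

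- RP2D 125 mg: 100, 75, 50. Three feasible reductions.
- RP2D 100 mg: 75, 50, 25. Three.
- RP2D 75 mg: 50, 25, 0. Two.
- RP2D 50 mg: 25, 0. One.
- RP2D 25 mg: 0. None.

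A third reduction needs RP2D − 75 > 0, so an RP2D of 100 or 125 mg. At 75 mg or below, the feasibility clause already holds patients to two or fewer, and the limits of three and of two do not diverge. Both 100 and 125 mg are live candidates: they are dose levels 2 and 3 of Table 1, and Section 9.1 allows levels 1 to 3 on treatment schedule B as well.

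**Step 4. Side check on the phase II decision rule.** With 44 patients and success declared for more than 24 responders (Section 14.0), the exact binomial gives:

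- alpha = P(X ≥ 25 | n = 44, p = 0.45) = 0.0775, against a stated 0.08;
- power = P(X ≥ 25 | n = 44, p = 0.65) = 0.901, so a type II error of 1 − 0.901 = 0.099, against a stated 0.1.

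The stated design is reproduced, and the number of reductions allowed does not enter it.

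**The case against.** The strongest reply is that Section 9.3.2 already supplies the exception that the Table 7 note leaves out. The exceptional-situations text is general, names the third reduction, and sends the decision to the lead investigator, which would tend to keep sites in line. The note also looks like shorthand. Its next sentence requires treatment to stop after a BGJ398 delay of more than 14 days, again without the exception that Section 9.3.2 gives for that same rule. Section 9.3.2 presents Table 7 as guidance, and the table's own column heading calls the modifications recommended. Finally, the general rule cites Table 6, so a careful reader could import the clear-benefit condition from there.

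Much of this stands. It is enough to reconcile the Table 7 note with Table 6, and it makes it less likely that the note was meant to override Section 9.3.2. It does not repair the general rule. Importing the condition from Table 6 narrows an allowance that the sentence gives to each patient subject only to feasibility, and the text still places the stopping point after three reductions.

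A reader might also infer that a fourth rule conflicts with these, namely that when "the same toxicity recurs with the same or worse severity, the patient must discontinue study treatment". The documents do not support that. The rule concerns recurrence of one toxicity after treatment has resumed at a lower dose, and its sentence goes on to allow continuation by agreement with the lead investigator. The other passages count reductions, which may come from different toxicities. A same-toxicity stop and a cap on the count can coexist.

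**Conclusion.** The inconsistency is real but narrow. The general rule in Section 9.3.2 cannot be reconciled as written with the conditional third step in Table 6 or with the limit in the Table 7 note. It has a practical effect only if the RP2D is 100 or 125 mg and a patient needs a third reduction. This rests on reading Table 6 literally in 25 mg steps from the RP2D.

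Two stronger conclusions should not be drawn. The first is that sites *will* stop treatment at different points. The documents support only that they could, since the RP2D may be 75 mg or lower and discussion with the lead investigator may remove the difference. The second is that the trial's result hangs on this because 24 and 25 responders fall on opposite sides of the cut-off. Any fixed threshold turns on one patient, so that says nothing about the size of this particular problem. The documents give no frequency of third reductions. Under the best-overall-response definition within 32 weeks in Section 12.1.11, a response already confirmed would not be undone by later stopping. Patients who have had one dose of the combination stay in the denominator (Section 14.0).

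The case for correction therefore rests on patient safety, compliance and consistent exposure. No effect on sample size, alpha or power is claimed.

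**What to change.** The sponsor should reconcile the general rule and the exceptional-situations paragraph of Section 9.3.2, Table 6 and the closing note to Table 7 into one statement of the number of BGJ398 reductions allowed. That statement should say whether the third is conditional. The Table 7 note should say whether the lead-investigator exception applies to it and should point to the governing text. Which limit is right is a clinical decision for the sponsor, and none is proposed here. The cost is protocol wording only, with no change to sample size, visits or analysis.

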9.4 Drug Interactions

In general, concomitant medications and therapies deemed necessary for the supportive care and safety of the patient are allowed, provided their use is documented in the patient records and on the appropriate case report form. The administration of any other anti-cancer agents including, chemotherapy and biologic agents is not permitted. Use of erythropoietin alfa (EPO) is allowed at the discretion of the treating investigator. G-CSF or GM-CSF may not be used as a prophylactic measure but may be used as otherwise clinically indicated to support blood counts for patients in this study. The use of other concurrent investigational drugs is not allowed.

Subjects should receive full supportive care during the study, including transfusion of blood and blood products, and treatment with antibiotics, analgesics, short course of steroids, or bisphosphonates, when appropriate. Anti-emetics (such as prochlorperazine, lorazepam, ondansetron or other 5-HT antagonists) may be administered prophylactically in the event of nausea. Antidiarrheals, such as loperamide, may be administered as needed in the event of diarrhea. Oral contraceptive pills are permitted.

MEMORIAL SLOAN-KETTERING CANCER CENTER IRB PROTOCOL

IRB#: 14-140 A (7)

All concomitant medications taken during the study will be recorded with indication, dose information, and dates of administration. The Electronic Data Capture system, MediData RAVE, must capture the concurrent use of all other drugs, over-the-counter medications, or alternative therapies. The MSKCC Principal Investigator should be alerted if the patient is taking any agent known to affect (or with the potential to affect) selected P450 isoenzymes.

All subjects will be asked to provide a complete list of prescription and over-the-counter medications that have been taken within the 4 weeks prior to screening. The investigator must be informed as soon as possible about any new medication(s) taken from the time of screening until the completion of the post-treatment follow-up visit. Additionally, patient nicotine history should be recorded as indicated on the eCRFs.

9.4.1 Permitted concomitant therapy with Imatinib requiring caution and/or action

Imatinib appears to be a competitive inhibitor of CYP2Cp, CYP2D6, CYP3A4/5, suggesting that imatinib could reduce the clearance of co-administered drugs whose metabolism is dependent on these P450 cytochrome isoenzymes. Because of the inherent risk of either reduced activity or enhanced toxicity of concomitant medications and/or imatinib, drugs known to be metabolized by the same P450 isoenzymes as imatinib should be used with caution (Appendix C). A non-comprehensive list of cytochrome CYP3A4 inhibitors and inducers may be found in Appendix C. FDA classification of CYP3A4 inhibitors can be found at:

<http://www.fda.gov/Drugs/DevelopmentApprovalProcess/DevelopmentResources/DrugInteractionsLabeling/ucm093664.htm#cypEnzymes>

A non-comprehensive list of CYP3A4 inducers is provided in Appendix C.

Special care has to be given to the concomitant use of acetaminophen (paracetamol, Tylenol) with imatinib. Any use of this drug has to be documented in the medical records and/or captured on the appropriate case report form. Patients should be warned to avoid or restrict the use of over-the-counter and prescription medicines containing acetaminophen (paracetamol).

Since warfarin is metabolized by CYP2C9 and CYP3A4, patients who require anticoagulation should receive low-molecular weight or standard heparin, if possible.

Patients should also avoid Seville oranges or Seville oranges derivatives, grapefruit or grapefruit juice, star fruit or star fruit juice and other foods known to inhibit CYP3A4 while taking imatinib.

Drugs that may increase imatinib plasma concentrations (Appendix C): Caution is recommended when administering imatinib with inhibitors of the cytochrome P450 isoenzyme CYP3A4 family (e.g., ketoconazole, itraconazole, erythromycin, and clarithromycin). Substances that inhibit CYP3A4 activity may decrease metabolism and increase imatinib concentrations. There was a significant increase in exposure to imatinib when the compound was co-administered with ketoconazole, a CYP3A4 inhibitor.

Drugs that may decrease imatinib plasma concentrations (Appendix C): Substances that are inducers of CYP3A4 activity may increase metabolism and decrease imatinib plasma concentrations. Co-medications that induce CYP3A4 (e.g., dexamethasone, phenytoin, carbamazepine, rifampicin, phenobarbital or St. John's Wort) may reduce exposure to imatinib.

MEMORIAL SLOAN-KETTERING CANCER CENTER
IRB PROTOCOL

IRB#: 14-140 A (7)

Drugs that may have their plasma concentration altered by imatinib (Appendix C): Imatinib increases the mean C_{max} and AUC of simvastatin (a CYP3A4 substrate) 2- and 3.5-fold, respectively, indicating inhibition of CYP3A4 by imatinib. Particular caution is recommended when administering imatinib with CYP3A4/5 substrates with a narrow therapeutic window (e.g., cyclosporine or pimozone). Imatinib will increase plasma concentrations of other CYP3A4 metabolized drugs (e.g., triazolobenzodiazepines, dihydropyridine calcium channel blockers, certain HMG-CoA reductase inhibitors, etc.).

9.4.2 Permitted concomitant therapy requiring caution and/or action with BGJ398

Drugs that alter the pH of the GI tract: BGJ398 is characterized by pH-dependent solubility, and therefore, medicinal products that alter the pH of the upper gastro-intestinal tract may alter the solubility of both compounds, and limit bioavailability. These agents include, but are not limited to, proton-pump inhibitors (e.g., omeprazole), H₂-antagonists (e.g., ranitidine) and antacids. Therefore, study drug(s) should be dosed at least 2 hours before or 10 hours after dosing with a gastric protection agent. Note that some proton-pump inhibitors may inhibit BCRP.

Corticosteroids: Chronic dosing of corticosteroids such as dexamethasone and prednisone is known to induce CYP3A enzymes, thereby increasing the risk of reducing drug exposure to sub-therapeutic levels. In addition BGJ398 is an in vitro inhibitor of CYP3A4 and has the potential to increase the systemic exposure of corticosteroids that are metabolized by CYP3A4. Systemic corticosteroid treatment can be used with caution and minimized to the extent possible.

Substrates and inhibitors:

CYP substrates and inhibitors:

BGJ398 was shown to inhibit the cytochrome p450 isoenzyme CYP3A4 in in-vitro assays, thus, suggesting an increased risk of drug interactions with concomitant medications that are metabolized by CYP3A4. However, such interactions have not been confirmed in patients. Therefore, investigators may administer medications that are known to be metabolized by CYP3A4. Patients must be monitored for potentiation of toxicity and may require dose titration or reduction of the CYP3A4 substrate. In particular caution is advised when substrates with a narrow therapeutic index, such as alfentanil, fentanyl, astemizole, cisapride, diergotamine, ergotamine, pimozone, quinidine, sirolimus, tacrolimus, and terfenadine need to be administered. Please refer to Appendix D for the list of medications to be used with caution.

Caution is advised when BGJ398 is co-administered with opioid analgesics. Inhibition of opioid metabolism by CYP3A4 can lead to opioid toxicity, including fatal respiratory depression, or an enhanced risk for QTc prolongation. Patients receiving BGJ398 and opioid analgesics should be carefully monitored. Synthetic opioids with clinically relevant interactions with CYP3A4 inhibitors include, but are not limited to, propoxyphene, fentanyl, alfentanil and sufentanil. Use of alfentanil, a sensitive CYP3A4 substrate with narrow therapeutic window, should be avoided whenever possible. The use of methadone and levomethadyl should also be avoided whenever possible. Refer to the Appendix D for the list of medications to be used with caution. Note that the list may not be comprehensive.

MEMORIAL SLOAN-KETTERING CANCER CENTER
IRB PROTOCOL

IRB#: 14-140 A (7)

Hormonal contraceptives may be affected by cytochrome P450 interactions and are therefore not considered effective for this study. For allowed contraception methods please refer to section 11.4.1. Highly effective contraception should be maintained throughout the study.

BGJ398 is a reversible inhibitor of CYP2C8, CYP2C9 and CYP2C19; coadministration of medications that are substrates or inducers of CYP2C are permitted. BGJ398 is a substrate of CYP3A4. Therefore moderate inhibitors and inducers should be used with caution if no other alternative is available. Strong inhibitors and inducers are prohibited.

Please refer to Appendix D for the list of medications to be used with caution and Appendix E for drugs that are prohibited to be used with BGJ398. Please note that the list might not be comprehensive.

Transporter substrates: In vitro data show that BGJ398 is an inhibitor of BCRP. CQM157, a metabolite of BGJ398, is an inhibitor of transporters P-gp, BCRP, OATP1B1, and OATP1B3 (IC₅₀ 2-4 μ M). In the absence of data confirming whether transporter interactions occurs in vivo, patients receiving medications that are substrate of these transporters must be monitored for potential toxicity and may require dose titration or reduction of the medication.

Non-enzyme Inducing Anti-epileptic drugs (non-EIAED): Non-enzyme inducing anti-epileptic medication (non-EIAED) such as valproic acid, levetiracetam and lamotrigine are allowed with caution. Patients who were previously on a non-EIAED and need to change anti-convulsants should be started on another non-EIAED if at all possible. EIAEDs are not permitted (Appendix E).

Anti-emetics: Anti-emetics are allowed for the treatment of nausea or vomiting. It is recommended to avoid using drugs that are known to cause QT prolongation. Note that some anti-emetics have a known risk for Torsade de Pointes, and therefore need to be used with caution. See Appendix D for list of drugs that need to be used with caution. Aprepitant is both a sensitive substrate and a moderate CYP3A4 inhibitor and can be used with caution if an alternative is not available.

QT/QTc interval prolongation or torsade de pointes medications: Medications that have the potential to prolong the QT/QTc interval or induce torsades de pointes are allowed with caution. Investigators at their discretion may co-administer such medications, but patients should be carefully monitored. See Appendix D for list of drugs that need to be used with caution.

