11.3 Pregnancy Testing, Prevention and Reporting

11.3.1 Pregnancy Testing and Prevention

The need for a screening pregnancy test depends on whether a female subject is of childbearing potential or non-childbearing potential.

A female of non-childbearing potential (i.e., physiologically incapable of becoming pregnant) is defined as any female who has had a hysterectomy, bilateral oophorectomy (ovariectomy) or bilateral tubal ligation, or is post-menopausal.

A practical definition accepts menopause after 1 year without menses with an appropriate clinical profile, e.g., age appropriate, >45 years in the absence of hormone replacement therapy (HRT). In questionable cases, the subject must have a follicle stimulating hormone (FSH) value >40 mIU/mL and an estradiol value < 40pg/mL (<140 pmol/L).

A female of child-bearing potential is defined as any female who does not meet the criteria of non-childbearing potential as described in the previous paragraph.

If a female subject is of childbearing potential, she must have a blood β -HCG pregnancy test performed within 14 days of the first dose of study treatment. Subjects with positive pregnancy test result must be excluded from the study. Subjects with negative pregnancy test result must agree to use an effective contraception method as described below from 14 days prior to the first dose of study treatment until 3 months following the last dose of study treatment.

Acceptable contraceptive methods, when used consistently and in accordance with both the product label and the instructions of the physician, are as follow:

- An intrauterine device with a documented failure rate of less than 1% per year.
- Vasectomized partner who is sterile prior to the female subject's entry and is the sole sexual partner for that female.
- Complete abstinence from sexual intercourse for 14 days before exposure to investigational product, through the dosing period, and for at least 21 days after the last dose of investigational product.
- Double-barrier contraception: condom and occlusive cap (diaphragm or cervical/vault caps) with a vaginal spermicidal agent (foam/gel/cream/suppository).
- Implants of levonorgestrel where not contraindicated for this patient population or per local practice
- Injectable progesterone where not contraindicated for this patient population or per local practice.
- Estrogenic vaginal ring
- Percutaneous contraceptive patches

MEMORIAL SLOAN-KETTERING CANCER CENTER IRB PROTOCOL

IRB#: 14-140 A (7)

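### Section 11.3.1 accepts four hormonal contraceptives that section 9.4.2 does not count as effective, and sections 6.1, 9.4, 9.4.2 and 11.3.1 need one consistent rule

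*Combined protocol and SAP*

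**What the plan says.** Four places in the protocol bear on contraception.

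- **Section 9.4.2** (concomitant therapy with BGJ398): "Hormonal contraceptives may be affected by cytochrome P450 interactions and are therefore not considered effective for this study". It asks for highly effective contraception throughout, and adds: "For allowed contraception methods please refer to section 11.4.1".
- **Section 11.3.1** (Pregnancy Testing and Prevention): "Subjects with negative pregnancy test result must agree to use an effective contraception method as described below", for the period "from 14 days prior to the first dose of study treatment until 3 months following the last dose of study treatment". The list that follows has eight methods, of which four are hormonal. The implant bullet reads "Implants of levonorgestrel where not contraindicated for this patient population or per local practice". The bullet for the injectable method reads "Injectable progesterone where not contraindicated for this patient population or per local practice". The ring is entered simply as "Estrogenic vaginal ring" and the patch option simply as "Percutaneous contraceptive patches". The abstinence option sets a minimum of 21 days after the last dose.
- **Section 6.1** (inclusion criteria) requires agreement to a reliable barrier method during treatment and for 3 months after it.
- **Section 9.4** (Drug Interactions) says, in its paragraph on supportive care, that oral contraceptive pills may be taken.

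On a confirmed pregnancy, 11.3.1 requires treatment to stop at once and refers to Section 12.0 for reporting. Section 12.0 contains the tumour response criteria.

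**The concern.** Section 17.0 excludes pregnant and lactating women because both drugs may harm a fetus or a nursing infant. The study calendars in 10.1.1 and 10.1.2 schedule one pregnancy test, at baseline, and leave later tests to the investigator's discretion. After enrolment, therefore, the contraception instruction is the main standing safeguard.

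That instruction is not consistent. A site reading 11.3.1 would tell a patient with a hormonal ring or patch that her method is acceptable. A site reading 9.4.2 would tell her that it does not count. A site reading 6.1 would tell her that she needs a barrier method whatever else she uses. No text says which section governs. If a pregnancy does occur, the site is told to report it but is sent to a section that does not say how.

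**Working it through.** No design figure is involved, so the check is a comparison of texts plus one subtraction.

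**Step 1. Classify the list in 11.3.1.**

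| Method | Hormonal | Own qualifier (contraindication or local practice) | Barrier required in the bullet |
|---|---|---|---|
| Intrauterine device | type not stated | no | no |
| Vasectomized partner | no | no | no |
| Abstinence | no | no | no |
| Double barrier | no | no | is itself a barrier |
| Levonorgestrel implant | yes | yes | no |
| Injectable progesterone | yes | yes | no |
| Estrogenic vaginal ring | yes | no | no |
| Patch | yes | no | no |

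Hormonal methods: 4 of 8, leaving the intrauterine device uncounted because its type is not given. Two of the four carry their own qualifier and two do not. None of the four bullets asks for an added barrier. A lead-in sentence makes all eight methods conditional on consistent use, the product label and the physician's instructions. Neither it nor the two qualifiers mentions the P450 concern in 9.4.2.

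**Step 2. Ask each section whether a hormonal method alone is enough.**

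- 11.3.1: yes, on its own terms.
- 9.4.2: no.
- 6.1: no, because a barrier method is required.
- 9.4: pills are permitted, without saying whether they count as contraception.

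Section 6.1 also raises a question of its own. Read literally, it asks for a barrier method from patients relying on an intrauterine device or a vasectomized partner, both of which 11.3.1 accepts without one.

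**Step 3. Compare the two periods in 11.3.1.** Taking 3 months as calendar months, the duty lasts 89 to 92 days after the last dose. The abstinence minimum is 21 days. The two differ by 89 − 21 = 68 to 92 − 21 = 71 days.

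**Step 4. Follow the pointers.** Section 9.4.2 points to 11.4.1, but in the supplied text Section 11 runs from 11.3.1 straight into Section 12.0. The only method list is the one that conflicts with 9.4.2. Section 11.3.1 points to Section 12.0 for pregnancy reporting, but that section covers response assessment. Section 17.2.1 excludes pregnancies from its 24-hour report to the manufacturer, and 17.2 to 17.4 give no procedure for reporting a pregnancy.

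**The case against.** The strongest reply is that 6.1 already closes the gap. The barrier criterion is part of eligibility, an eligibility checklist is completed at registration (15.1), and requests to deviate from eligibility are not allowed (16.3.2). Read as a whole, the protocol lets a hormonal method be used only alongside a barrier. This stands as mitigation: a reader might infer that patients may rely on a hormonal method alone, and the whole protocol does not support that. It does not make 9.4.2 and 11.3.1 agree.

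A reader might also infer that a patient can comply with 11.3.1 by ending abstinence at day 21. The text does not support this. The parent sentence keeps the 3-month duty in force, and the bullet sets only a minimum. A patient who stops at day 21 and uses no other method breaks 11.3.1 as well as 6.1. What remains is an inconsistency that invites misreading.

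Nor do the documents show that hormonal methods fail with these drugs. Sections 9.4.1 and 9.4.2 describe inhibition of CYP3A4, and 9.4.2 says the BGJ398 interactions are unconfirmed in patients. The statement in 9.4.2 is precautionary, so the documents do not settle which section should yield. Deleting the hormonal methods is one solution and not the only one.

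The line on oral pills in 9.4 can fairly be read as a permission for concomitant medication only. It still needs to say so.

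On reporting, a congenital anomaly or birth defect is a serious adverse event under 11.2.2 and 17.2, so that outcome has a route. The pregnancy itself has none.

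**Conclusion.** The concern holds as a conflict between safety instructions. Four of the eight methods accepted in 11.3.1 are of a kind that 9.4.2 does not count as effective. Criterion 6.1 mitigates this but leaves 6.1, 9.4.2 and 11.3.1 giving different answers. The 21-day minimum is inconsistent with the 3-month duty in the same section, which nevertheless governs; the 68 to 71 days are the difference between two stated periods, not a permitted lapse. Two cross-references are wrong in the supplied text, and no pregnancy-reporting procedure appears there.

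These are counts of list items and days. The number of patients affected cannot be derived from the documents, and no contraceptive failure is shown. The endpoint, sample size and error rates are untouched. The conclusion assumes that the four named methods are hormonal and that 3 months means calendar months. It should be fixed because it concerns fetal exposure and the remedy is cheap.

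**What to change.** - **11.3.1, methods.** Allow the implant, injectable, ring and patch only together with a barrier method, which matches 6.1, or delete them. State how the barrier rule in 6.1 applies to the intrauterine device and vasectomized-partner options.
- **11.3.1, abstinence.** Change 21 days to 3 months.
- **9.4.** State that oral contraceptives are permitted as concomitant medication but do not count as effective contraception for this study.
- **9.4.2.** Correct the reference from 11.4.1 to 11.3.1.
- **11.3.1 and Section 17.** Replace the reference to Section 12.0 with one to a short new procedure in Section 17: who reports a pregnancy, to whom, by when, and with follow-up to outcome.

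The cost is protocol wording in 9.4, 9.4.2, 11.3.1 and Section 17. The design, sample size and visit schedule do not change. Whether the consent form needs a matching change cannot be judged, because it was not supplied.
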